### **3.2.28 Modified ASAS Classification Criteria**

If the results for CRP, human leukocyte antigen B27 (HLA-B27) or MRI on the 'Modified ASAS Classification Criteria for AS' eCRF differ from central laboratory results and/or the MRI result from central review, respectively, the result of the central laboratory and/or central review of MRI will be used in the summary table for modified ASAS classification criteria.

### **3.2.29 Past, prior and concomitant medications**

Medication taken before the date of first study drug administration in Part A (regardless of continuing or stopping the medication) will be considered as prior medication in Part A.

Prior medication in Part A, stopping before the first study drug administration in Part A will be considered as 'past medication'.

Prior medication in Part A not stopped before first study drug administration in Part A will be considered as concomitant medication during Part A. Medication for which the start date is between the first date (including the date) of study drug administration in Part A and the date of the last study drug administration in Part A + 14 days (including the date) and prior to the date of first study drug administration in Part B if any, will also be considered as concomitant medication during Part A.

Medication taken before the date of first study drug administration in Part B (regardless of continuing or stopping the medication) will be considered as prior medication in Part B.

Prior medication in Part B not stopped before first study drug administration in Part B will be considered as concomitant medication during Part B. Medication for which the start date is between the first date (including the date) of study drug administration in Part B and the date of the last study drug administration in Part B + 14 days (including the date) will also be considered as concomitant medication during Part B.

In subjects experiencing a flare in Part B, a concomitant medication during Part B taken before the date of flare (regardless of continuing or stopping the medication) will be considered pre-flare concomitant medication in Part B. Concomitant pre-flare medication in Part B not stopped before the date of flare will be considered as post-flare concomitant medication during Part B. In subjects experiencing a flare in Part B, medication for which the start date is after or on the date of flare will also be considered as post-flare concomitant medication during Part B.

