The study design has three different periods: Part A, Part B and Escape Part. The outputs will be presented for each period. Summaries for Part A will be presented by axSpA subpopulation. Summaries for Part B will be presented by treatment group excluding any post-flare assessments in the subset of subjects experiencing a flare in Part B and start escape therapy. For the subset of subjects experiencing a flare in Part B and start escape therapy, separate summaries will be produced for the Escape Part.

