#### **6.4 Past, prior and concomitant medications**

Past medication summaries will be generated for disease-modifying antirheumatic drugs (DMARDs), non-steroidal anti-inflammatory drugs (NSAIDs), and anti-tumor necrosis factors (anti-TNFs) by anatomical therapeutic chemical (ATC) code (level 3 (4-digit) decode, level 4 (5-digit) decode, and PT). See Section 3.2.29 for definition of past, prior and concomitant medications.

For Part A, prior DMARDs and NSAIDs will be summarized by WHO-DD ATC code (level 3 (4-digit) decode, level 4 (5-digit) decode, and PT). No extra table for prior anti-TNFs will be produced due to the fact that this summary is identical to the 1 for the past anti-TNFs.

Summaries will be presented by axSpA subpopulation and overall using the SS.

For Part A, prior medications (except DMARDs and NSAIDs) will be summarized by WHO-DD ATC code (level 2 (3-digit) and level 3 (4-digit) decode. Summary will be presented by axSpA subpopulation and overall using the SS.

For Part A, concomitant DMARDs and NSAIDs will be summarized by WHO-DD ATC code (level 3 (4-digit) decode, level 4 (5-digit) decode, and PT). Summaries will be presented by axSpA subpopulation and overall using the SS.

For Part A, concomitant medication (except DMARDs and NSAIDs) will be summarized by WHO-DD ATC code (level 2 (3-digit) and level 3 (4-digit) decode. Summary will be presented by axSpA subpopulation and overall using the SS.

For Part B, prior DMARDs and NSAIDs will be summarized by WHO-DD ATC code (level 3 (4-digit) decode, level 4 (5-digit) decode, and PT). Summaries will be presented by treatment group and overall using the SSB.

For Part B, prior medications (except DMARDs and NSAIDs) will be summarized by WHO-DD ATC code (level 2 (3-digit) and level 3 (4-digit) decode. Summary will be presented by treatment group and overall using the SSB.

For Part B, concomitant DMARDs and NSAIDs will be summarized by WHO-DD ATC code (level 3 (4-digit) decode, level 4 (5-digit) decode, and PT). Summaries will be presented by treatment group and overall using the SSB. Additionally, in subjects experiencing a flare in Part B, separate summaries by treatment group using the ETS will be provided presenting pre-flare and post-flare concomitant medications.

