For Part B, concomitant medications (except DMARDs and NSAIDs) will be summarized by WHO-DD ATC code (level 2 (3-digit) and level 3 (4-digit) decode. Summary will be presented by treatment group and overall using the SSB. Additionally, in subjects experiencing a flare in Part B, separate summaries by treatment group using the ETS will be provided presenting pre-flare and post-flare concomitant medications.

Prohibited medication use and date of first usage will be determined and documented during the pre-analysis review meeting prior to the database lock.

The number and percentage of subjects who used prohibited medication will be summarized by axSpA subpopulation and overall in Part A using the SS and by treatment group and overall in Part B using the SSB. Separate summaries in subjects experiencing a flare in Part B by treatment group using the FS will be provided presenting pre-flare and post-flare prohibited medication. An overall summary of subjects who used prohibited medication in Part A or Part B will be provided using the SS.

Prohibited medications will be assigned to Part A or Part B (overall, pre-flare, post-flare) using the same rules as outlined for concomitant medications in Section 3.2.29 .

Prior and concomitant medications and prohibited medications will be listed using the SS.

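### As written, the by-arm Part B concomitant and prohibited medication tables include drugs started on escape CZP, which conflicts with Section 3.1 and with the escape cut-off used elsewhere in the SAP

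*SAP*

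**What the plan says.** SAP Section 3.2.29 counts two kinds of drug as concomitant in Part B: those still in use at the first Part B dose, and those started from that dose up to "the last study drug administration in Part B + 14 days (including the date) will also be considered as concomitant medication during Part B". It then divides this category for subjects who flare. A drug begun on or after the flare date "will also be considered as post-flare concomitant medication during Part B", so the post-flare drugs are a subset of the Part B drugs.

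Section 6.4 uses the category for NSAIDs and DMARDs ("Summaries will be presented by treatment group and overall using the SSB") and, on the same set, for other concomitant drugs and prohibited drugs. Escaped subjects get an addition: "separate summaries by treatment group using the ETS will be provided presenting pre-flare and post-flare concomitant medications". For prohibited drugs the corresponding addition uses the Flared Set, and the assignment rule names a whole-of-Part-B category: "Prohibited medications will be assigned to Part A or Part B (overall, pre-flare, post-flare) using the same rules as outlined for concomitant medications".

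Section 3.1 points the other way: "Summaries for Part B will be presented by treatment group excluding any post-flare assessments in the subset of subjects" who flare and start escape therapy. It speaks of assessments and does not say whether medications are covered.

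**The concern.** Flare is defined on ASDAS. Four of its five components are patient-reported (back pain, duration of morning stiffness, peripheral pain or swelling, global activity). A reader would naturally look at the NSAID, DMARD and prohibited-drug tables to see whether background treatment was similar across arms while subjects were on randomised treatment. As defined, those tables mix randomised treatment with escape. A placebo subject who starts an NSAID months after moving to CZP is counted in the by-arm Part B table. Placebo is the arm expected to escape most, so the mixing differs by arm. What is at stake is how descriptive tables are read, not a test.

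**Working it through.** **1. Does the Part B window include escape?**
- Section 3.2.29 gives no cut at escape and places post-flare drugs inside the Part B category.
- Section 6.4 lists a Part B overall category beside pre-flare and post-flare for prohibited drugs.
- Section 10.1.2.1 has to add a limit at the start of escape to restrict Part B injections, so an unrestricted Part B injection includes escape dosing.

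**2. How are other data handled?** Each of these sections separates escape explicitly; Sections 3.2.29 and 6.4 do not do so for the SSB medication tables.
- Resource use (3.2.17): events after the first escape injection are excluded from the Part B tables.
- Compliance (7): escape injections are not considered in Part B.
- Exposure (10.1.2.1): limited to dosing before escape and censored at its start.
- Adverse events (10.2): post-flare events are excluded from the Part B prior-to-flare tables, with the split at the start of escape therapy.

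**3. Can the missing table be rebuilt from the planned ones?** Use before escape in all SSB subjects equals users among non-escapers plus pre-escape users among escapers. Users among non-escapers equal the SSB total minus the escapers who used the drug at any time. That last count is pre + post − both, and the number in both is not tabulated (a continuing drug counts on both sides). So the planned tables cannot give it. The listings can, with new programming.

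**4. The plan's own figures.** Section 2.4 assumes flare-free proportions of 80%, 75% and 45% (Q2W, Q4W, placebo), 70 per group, two-sided 0.05, and states 98% and 94% power. A pooled normal approximation gives 99.4% and 96.0%; with continuity correction it gives 98.9% and 94.1%; Fisher's exact test gives 98.9% and 94.0%. The stated figures are reproduced to within 2 points and are not in dispute. Only the flare rates are used below.

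**5. Upper bound on contributors:** 70 × (1 − flare-free proportion).
- Placebo: 70 × 0.55 = 38.5
- Q4W: 70 × 0.25 = 17.5
- Q2W: 70 × 0.20 = 14

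These are upper bounds because Section 3.2.22 also counts withdrawals and repeated missing ASDAS as flares, and not all of those subjects escape.

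**6. Illustration of the distortion.** Assume 40% use in every arm before escape, and that a share q of escaping non-users start the drug on escape. The table then shows 40% + 60% × flare proportion × q.

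| q | Placebo | Q4W | Q2W | Placebo − Q2W |
|---|---|---|---|---|
| 0.1 | 43.3% | 41.5% | 41.2% | 2.1 points |
| 0.3 | 49.9% | 44.5% | 43.6% | 6.3 points |
| 0.5 | 56.5% | 47.5% | 46.0% | 10.5 points |

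A table cut at escape would show 40% in each arm. Neither the 40% nor q comes from the SAP.

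**7. What the cut does to observation time.** Assume constant hazard λ = −ln(S)/48 per week, escape 2 weeks after flare, and all flares escaping. Mean escape time to Week 96 is 46 − (1 − e^(−46λ))/λ, which is 13.9, 5.8 and 4.6 weeks (placebo, Q4W, Q2W). Time left on randomised treatment:
- Placebo: 48 − 13.9 = 34.1 weeks
- Q4W: 48 − 5.8 = 42.2 weeks
- Q2W: 48 − 4.6 = 43.4 weeks

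**The case against.** The strongest reply is that the wording is ambiguous rather than wrong. Section 3.1 names Part B and the Escape Part as separate periods. The stop-date imputation rules in Section 4.2 distinguish the last Part B administration, for subjects without a flare, from the last escape administration. On that usage the window could end 14 days after the last randomised dose. This shows a conflict but does not remove it: Section 3.2.29 still calls post-flare drugs Part B drugs, and Section 6.4 still has an overall category.

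Several further objections stand:
- A reader might infer that background use cannot be compared between arms at all. The SAP does not support that. Prior NSAIDs and DMARDs in Part B are tabulated by arm for the whole SSB, escapers have pre-flare and post-flare tables by arm, non-escapers' records contain no escape time, and everything is listed.
- A reader might infer that the pre/post split is misplaced because it is made at flare ("medication for which the start date is after or on the date of flare will also be considered as post-flare concomitant medication") while escape normally begins up to 2 weeks later. That split is defensible. For the question of whether a drug influenced the flare, one started afterwards could not have done so.
- Share of subject-time on escape is not the bias. A drug already in use before escape counts under either window; only new starts on escape matter.
- Q2W subjects who escape keep their allocated regimen (Section 2.3.3), so the change of CZP regimen concerns placebo and Q4W. Section 3.7 assigns SSB columns by actual Part B treatment, without saying how that applies to a placebo subject who later receives CZP.
- Cutting at escape creates its own imbalance: crude percentages would then cover less time in placebo.

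**Conclusion.** The point holds as an unreconciled definition with a practical consequence. As written, the SSB by-arm concomitant and prohibited medication tables include drugs started on escape. This conflicts with Section 3.1 and with four other parts of the SAP, and no planned table shows use on randomised treatment for all treated subjects by arm.

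Up to 38.5, 17.5 and 14 of 70 subjects (placebo, Q4W, Q2W) could contribute escape-period drugs, given the planning flare rates and every flare leading to escape. The spurious placebo–Q2W gap of about 2 to 10.5 points is illustrative only, since the rate of new starts on escape is not known.

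A reader might take this further, to a bias in the primary result. The documents do not support that: the tables are descriptive and no test uses them. Per-protocol exclusions rest on deviations agreed at the data review before lock, where prohibited use and its first date are also documented.

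**What to change.** In Sections 3.2.29 and 6.4, for subjects who escape, end the concomitant and prohibited medication window for the SSB by-arm Part B tables on the day before the first escape dose. State in Section 3.1 that its post-flare exclusion covers medications. With that cut, these tables also no longer mix placebo or Q4W treatment with escape CZP in one subject's record.

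Report the tables with subject-time from the first Part B dose to the end of that window, or per 100 patient-years, because the cut shortens observation most in placebo.

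Keep the pre/post tables on the Escape Therapy Set and the Flared Set, and state explicitly whether they split at the flare date or at the first escape dose. Either can be justified.

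The cost is SAP wording, one date cut-off in the medication dataset and a matching subject-time denominator. No new data are needed.

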### **3.3 Analysis time points**

The analysis time point of interest for Part A is Week 48. Additional time points of interest for Part A are the Screening Visit, Week 0, Week 2, Week 4, Week 12, Week 24, Week 32 and

Week 36. For subjects who withdraw early during Part A, data recorded at the Withdrawal Visit will be assigned to what would have been the next scheduled visit for the particular assessment that is being summarized, unless otherwise specified. These data will be included in the summaries of the assigned visit and the “Early Withdrawal” visit if applicable. If a subject withdraws early during Part A but does not have a Withdrawal Visit in Part A, safety and efficacy data recorded at either the date of the last scheduled or unscheduled visit during the treatment Period, whichever is later, will be included in summaries of “Early Withdrawal” visit. Only post Part A Baseline assessments will be included in the “Early Withdrawal” visit.

The analysis time point of interest for Part B is Week 96. Additional time points of interest for Part B are Week 48, Week 50, Week 52, Week 54, Week 56, Week 58, Week 60, Week 62, Week 64, Week 66, Week 68, Week 70, Week 72, Week 74, Week 76, Week 78, Week 80, Week 82, Week 84, Week 86, Week 88, Week 90, Week 92 and Week 94. For subjects who complete Week 96, safety and efficacy data recorded at a Week 96/withdrawal Visit will be included in summaries of the Week 96 visit and the “Last/Withdrawal” visit if applicable. For subjects who withdraw from Part B prior to Week 96, data recorded at the Withdrawal Visit will be assigned to what would have been the next scheduled visit for the particular assessment that is being summarized, unless otherwise specified. These data will be included in the summaries of the assigned visit and the “Last/Withdrawal Visit” if applicable. If a subject withdraws early during Part B but does not have a Week 96/withdrawal Visit, then safety and efficacy data recorded at either the date of the last scheduled or unscheduled visit during the treatment Period, whichever is later, will be included in summaries “Last/Withdrawal Visit”. For subjects experiencing a flare, the last visit prior to escape medication (e.g. Escape Week 0) will be included in the summaries of the “Last/Withdrawal Visit”. Only post Part B Baseline assessments will be included in the “Last/Withdrawal Visit”.

The analysis time point of interest for subjects experiencing a flare in Part B is Escape Week 12. Additional time points of interest for this set of subjects are Escape Week 0, Escape Week 2, Escape Week 4, Escape Week 6, Escape Week 8, Escape Week 10, Escape Week 24, Escape Week 36 and the final assessment visit as laid down for Week 96. For subjects who complete the final assessment visit as laid down for Week 96, safety and efficacy data recorded at this visit will be included in summaries of the “Last Visit (Week 96 Termination)” visit and the “Last/Withdrawal Escape” visit if applicable. For subjects who withdraw prematurely from the Escape Part, data recorded at the Withdrawal Visit will be assigned to what would have been the next scheduled visit for the particular assessment that is being summarized, unless otherwise specified. These data will be included in the summaries of the assigned visit and the “Last/Withdrawal Escape” visit if applicable. If a subject withdraws early during the Escape Part but does not have a Withdrawal Visit, then safety and efficacy data recorded at either the date of the last scheduled or unscheduled visit during the Escape Part, whichever is later, will be included in summaries “Last/Withdrawal Escape” visit. Only post Flare baseline assessments will be included in the “Last/Withdrawal Escape” visit.

All visit measurements, even violating the visit window, will be utilized for the respective visit as long as they are in the proper sequence. In case of repeated assessments at a particular visit, the last assessment will be used for visit presentation in by-visit summaries (except unscheduled repeats of Week 96).

#### PK and ADAb

For ADAb data the same approach as for the efficacy analysis will be used, i.e for withdrawals to assign the withdrawal value to the next scheduled visit for the assessment. However, for PK analysis the withdrawal PK result will be only included in summaries of “Withdrawal” and the “Withdrawal Escape” and not assigned to the next scheduled visit. Furthermore, the Withdrawal summaries visit will not summarize any last visit assessments.

In addition, in the case that a sample is collected one or more days following the scheduled visit date, in which the drug was administered, the PK results for that sample will not be summarized as part of that visit.

### 3.3.1 Relative day

The relative day will be included in different listings as appropriate.

For Part A, relative day, identified as “relative day [a]”, will be calculated relative to the first CZP administration in Part A. Relative day [a] will be calculated as follows:

Relative day [a] of date X = date X - Date of first CZP administration in Part A+1 if date X is on or after date of first CZP administration in Part A.

Relative day [a] of date X = date X - Date of first CZP administration if date X is before date of first CZP administration in Part A. Relative day [a] before first CZP administration in Part A will have the prefix “-”.

Relative day [a] after last CZP administration in Part A will have the prefix “+”, and will be calculated from the date of last CZP administration in Part A (date X - date of last CZP administration in Part A).

For Part B, relative day, identified as “relative day [b]”, will be calculated relative to the first study medication administration in Part B. Relative day [b] will be calculated as follows:

Relative day [b] of date X = date X - Date of first study medication administration in Part B+1 if date X is on or after date of first study medication administration in Part B.

Relative day [b] of date X = date X - Date of first study medication administration if date X is before date of first study medication administration in Part B. Relative day [b] before first administration of study medication in Part B will have the prefix “-”.

Relative day [b] after last study medication administration in Part B will have the prefix “+”, and will be calculated from the date of last study medication administration in Part B (date X - date of last study medication administration in Part B).

For subjects experiencing a flare and starting escape therapy, an additional relative day, identified as “relative day [f]”, will be calculated relative to the first study escape therapy administration in Part B. This additional relative day [f] will be calculated as follows:

Relative day [f] of date X = date X - Date of first study escape therapy administration in Part B+1 if date X is on or after date of first escape therapy administration in Part B.

Relative day [f] of date X = date X - Date of first escape therapy administration if date X is before date of first escape therapy administration in Part B. Relative day [f] before first escape therapy administration in Part B will have the prefix “-”.

Relative day [f] after last escape therapy administration in Part B will have the prefix “+”, and will be calculated from the date of last escape therapy administration in Part B (date X - date of last escape therapy administration in Part B).

Calculations of “Relative Day” will not include partial dates, but will be left blank in these instances.

### **3.3.2 End date of the Treatment Period**

The end date of the treatment Period will be either Week 48 for subjects who completed Part A and did not meet the criteria to be randomized into Part B, Week 96 for subjects completing the treatment Period of Part B, or the date of the Withdrawal Visit for subjects who discontinued during the treatment Period (whether Part A or Part B). If a subject does not have a Week 96/Withdrawal Visit or has visits after Week 96 due to escape treatment, then either the date of the last scheduled or unscheduled visit during the treatment Period or the date of last known dose of study drug during the treatment Period, whichever is later, will define the end date of the treatment Period.

